A collaboration has now been formed between [name] and Drs [name] and [name] of the UPEI Centre for Health and Community Research (CHCR) that will bring CBT4CBT to Canada. While CBT4CBT has previously been tested in urban areas, there are many advantages to offering computer-based training to more rural populations (such as PEI). These more remote areas frequently suffer from a lack of services, as well as a lack of continuity with the services currently offered. CBT4CBT may very well provide that needed continuity to Addictions treatment and has also been shown to improve retention.

3. BACKGROUND, RATIONALE AND STATEMENT OF RESEARCH QUESTION(S):

CBT4CBT will be the first computer-based, cognitive behavioural therapy program for Addictions treatment to be offered in Canada. CBT4CBT has been rigorously tested in urban populations in the United States but this collaboration will be the first pilot trial in First Nation and other rural communities in Canada. Prince Edward Island has a self-proclaimed need for innovative new substance abuse treatments and CBT4CBT may provide the continuity and retention to traditional therapy programs that current available treatment options often lack. This study will allow CBT4CBT to be tested in several Prince Edward Island communities to gage its efficacy and effectiveness. The results and feedback received from the pilot study will allow the program to be adapted for Canadian populations in order to optimize its positive outcomes within Canada.

CBT4CBT has been tested in urban populations in the United States in three rigorous randomized clinical trials with great success. The nature of CBT4CBT suggests it would also be beneficial in rural and remote populations which are common across Canada. Computer based treatments are cost-effective and although their nature necessitates human participants they have minimal risk associated with them. As the first computer based training for Addictions in Canada this research project could have broad implications for treatment in Addictions across our country.

Analysis techniques will be based on those used in previous CBT4CBT trials conducted by our collaborator, [name].

The primary substance abuse outcomes (self-reported abstinence) will be assessed throughout the study and through a six month follow-up. Additional outcomes will include use of other services (medical, legal), patient and provider satisfaction, as well as the costs of implementing the program. Each week, the counsellors will deliver a questionnaire (provided by the CHCR) which covers this range of topics to their patient participating in the trial. The data will be analyzed with a focus on feasibility (retention in both conditions, levels of substance abuse, health problems, and cost by condition).

4. SUBJECT SELECTION:

Participants will be recruited from Prince Edward Island; Lennox Island Health Centre and Abegweit Health Centre, Mount Herbert Provincial Addictions Treatment Facility Transition Unit and Methadone clinic, Holland College Student Services, University of Prince Edward Island Student Services, Charlottetown Methadone Clinic and Prince County Hospital. At RECAP in New Brunswick and Ontario Shores Mental Health Centre in Ontario.

A total of 240 Participants will be recruited during years 1-2 and an additional 440 participants will be recruited during years 3-4 ending in April 2019.

Counsellors already employed by the Centres will recruit participants who are willing to consent to a randomized trial of CBT4CBT. In order to create as representative a sample as possible, the inclusion criteria will be fairly broad, including any consenting individual who reports substance abuse in the past thirty days. Individuals who are currently suicidal, homicidal, or require immediate hospitalization will be excluded.

The participants will be patients who have reported substance abuse in the past thirty days. For the initial trial, all participating individuals will be over eighteen years of age and be approved to participate by their addictions counsellors.

Counsellors will ask individuals seeking treatment for substance abuse if they would be interested in learning about and participating in a substance abuse treatment project. If yes, participants will be introduced to the study Research Assistant who will go through the consent form(attached) with them. The Research Assistant will orally read the forms if necessary and individuals will be informed of their right to withdraw from the program should the need arise.

5. RESEARCH PLAN:

The individuals recruited for this study will each fall into one or more subgroup of the trial (transitioning patients [inpatient to outpatient], youth [18-24 years], maintained on methadone, and indigenous individuals) and will be analyzed individually as well as collectively by compiling results from all sites. A subgroup analysis based on gender is also planned to investigate any differences in outcomes between male and female participants, these two groups, historically, can show significant differences in response to mental health and addictions treatment.

Participants will be randomized to either test or control groups. Participants in the control group will receive treatment as usual (the conventional treatment offered at that site) and will also meet with the Research Assistant during week 4 and week 8 to complete questionnaires (attached) either in hard copy or online on a tablet provided. These participants will also be contacted six months after their eight-week participation in the trial ended to complete a follow-up questionnaire.

Participants randomized to the test group will receive treatment as usual but will also be asked to spend at least thirty minutes per week using the program. CBT4CBT use by each participant will be monitored throughout the trial to ensure that this requirement is being met. They may choose to do this on location at the site or from their personal computer/tablet. The individuals in this arm of the trial will also meet with a Research Assistant once a week for eight weeks to complete questionnaires and will be contacted six months after their eight-week participation in the trial ended to complete a follow-up questionnaire. These questionnaires can be completed online. Each participant will be asked to participate in the eight-week long treatment period regardless of group (test or control). In addition to participants' treatment as usual, this will involve a

commitment of approximately 10 minutes as a weekly average from participants in the control group, and approximately 45 minutes as a weekly average from participants in the test group. Please see the consent form table outlining the time commitments in more detail.

This trial design will mirror the designs in the trials already successfully conducted in the United States. Once an individual consents to participate, the counsellor will contact the Research Assistant who will meet with the individual and assign them a participant number generated using Randomizer.org (Geoffrey C. Urbaniak, 2015). This number will have been previously assigned to either test or control. The participant will be notified about the trial arm that they are placed into so that their participation may commence.

A Research Assistant will deliver the questionnaires to the trial participants. Questionnaires may be answered in hard copy or online in private. This removes the pressure from the participants to 'improve' in the eyes of their counsellor. Other than the addition of sections specifically relating to the CBT4CBT program, the questionnaires between groups will be identical.

As mentioned above, three previous/pilot studies in urban areas of the U.S. have been performed ([name] et al., 2008, 2009, 2014). The trial described herein will follow a very similar design.

Questionnaires, data analysis and protocols are based on those previously used by our collaborator in the US and have all been tailored to better suit Canadian populations. Based on the significant success that [name] had using these outcomes, tools and protocols we are confident in their reliability and validity.

Individuals who consent to this trial will be notified at the beginning of the trial that they have the right to remove themselves from the trial at any time. They also have the right to contact their counsellor or either co-investigator (phone numbers and emails provided on the consent form) at any time should they have questions or concerns. The counsellors also hold the ability to remove any of their patients from the trial at any time if they see fit.

6. ANALYSIS OF DATA:

Statistical analysis techniques previously used by the Co-Investigator [name] and her team will be performed on the generated data from this trial ([name] et al., 2008, 2009, 2014). These include one and two-way analysis of variance (ANOVA's) where appropriate. This will ensure a relevant analysis approach is used for the field of addictions treatment research as well as ensuring that the generated results may be compared with those previously established at other sites.

The power calculations performed to calculate the sample size are based on three similar published trials of CBT4CBT in urban populations in the US. Primary outcome measurements of this trial will be a subset of measurements collected in these previous trials. We believe retention and follow up rates will be similar if not higher than the previous trials as PEI has a less transient community than most urban centers like Connecticut. Based on the three previous trials ([name] et al., 2008, 2009, 2014), the average drug use measurement (measured by the percent days abstinence from all drugs) in the test groups was 75% and control group 66% with a common standard deviation of 24% at the end of the eight week trial. Retention during the eight week trial was on average 77% and follow-up success was approximately 87% six months post trial. These values were used to calculate the sample size of 30 (for each group) to achieve statistical significance with an alpha of 0.5 and a power of 0.8 for subgroup analysis of the initial trials on PEI, and an alpha 0.05 and a power of 0.8 for combined analysis (i.e. combining results from

all 240 participants across the four trial settings). Power calculations to achieve statistical significance with an alpha of 0.05 and a power of 0.9 were calculated for the large-scale effectiveness trials and a sample size of 110 was found.

Primary outcomes measured include retention, changes in drug use, changes in health (e.g. medical visits, family and social satisfaction, etc.) and program implementation costs. The outcomes to be determined are identical in the four parallel trials to foster comparability across populations.

Secondary outcomes measured include feedback from patients and counsellors. This information will be used to refine CBT4CBT as an ideal treatment approach for each relevant population. Analysis of this data will be on a qualitative level. Drs [name], [name] and [name] place a high priority on patient feedback and advisement and are in agreement that the patients who participate in these trials can contribute to quality improvement at both the individual and collective level. The populations in which CBT4CBT will be implemented throughout this program may have differing needs and desires for substance abuse treatment. [name] and her team to date have created three versions of the CBT4CBT program (drug abuse, alcohol only abuse, and a culturally specific version for Spanish speaking individuals in the U.S.). With the feedback from this initial trial, we aim to create potentially revised versions of the CBT4CBT program, which are tailored to better suit Canadian, specifically First Nation, youth, and rural/remote environments.

7. RISKS AND BENEFITS:

CBT4CBT has been shown to hold no more than minimal risk for all participants. In all previous trials, no adverse effects were demonstrated. For this implementation, all participants will be referred to the trial at the sole discretion of their counsellor and anyone who is deemed suicidal, homicidal, has an undiagnosed psychiatric disorder, or is requiring immediate hospitalization will be excluded. If at any point throughout the trial a participant wishes to withdraw, or if the counsellor feels they should be withdrawn from the trial, exposure to CBT4CBT will be immediately withdrawn.

CBT4CBT has demonstrated excellent results in improving retention and in allowing participants to significantly reduce their substance abuse. The goal of these initial trials is to have CBT4CBT become a standard treatment option in Mental Health and Addictions treatment programs throughout Canada by providing refined, or potentially new, versions of the program to populations across the country. This may significantly increase the success of addictions treatment across Canada and in turn largely benefit our society as a whole.

Participants in the 'test' group who respond well to CBT4CBT will have the opportunity to continue accessing the program at their leisure (using their provided login information) beyond the time frame of the study. Participants in the 'control' group may have the opportunity to access CBT4CBT once the trial is complete and assuming that positive effects of CBT4CBT are verified on PEI.

8. CONFIDENTIALITY:

The CHCR team currently work with Health PEI and the PEI Department of Health and Wellness on a CIHR-funded initiative which built the UPEI Secure Island Data Repository on the UPEI campus which holds de-identified PEI health records as well as any research-generated data from clinical trials such as this one. Therefore, the non-identifiable data generated

throughout this study will be stored, after collected and analysed, on secure servers in the UPEI Secure Data Facility. Only CHCR researchers (via password protection and key codes to the room) will have access to the data. All Data will be retained for a minimum of five years.

9. LIABILITY:

N/A

10. DISCLOSURE OF ANY FINANCIAL COMPENSATION:

N/A

11. REFERENCES:

Attached

12. APPENDICES:

Questionnaires or measuring instruments and appropriate copyright release (if applicable) should be included as appendices to the proposal when appropriate.

Any advertisements intended for use to recruit participants should be submitted for review.

Please see the General Guidelines (Section 3.11) concerning Advertisements.

Administrative Requirements for Research Protocols:

- Please use a font-size large enough to be legible (12pt Times New Roman font is preferred).
Protocols may be returned if this criterion is not met.
- Please include page numbers, as well as a version number and date on your proposal (which must be revised whenever the proposal is amended) and any appended data collection tools or measures.

Additional Considerations:

- Submissions based on a grant proposal (e.g. CIHR, PEI Research Fund), the level of data might not in all instances provide enough information about the methodology to meet the REB's requirements for ethical and scientific review. In these cases the grant proposal should be supplemented by further information based on the guidelines of the this REB.
- All documentation that will be provided to family doctors, participants, participant relatives and caregivers (including study introductory letters) must be reviewed and approved by the REB prior to use.

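### Four population tests and a combined test are planned with no order, shared alpha or exploratory label: even at two-sided 0.05 each, about 16% to 20% chance of a false significant result, about half favouring the program

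*Combined protocol and SAP*

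**What the plan says.** Section 5 names four populations: patients moving from inpatient to outpatient care, youth, people maintained on methadone, and indigenous individuals. Participants "will each fall into one or more subgroup of the trial", so membership can overlap. The populations "will be analyzed individually as well as collectively by compiling results from all sites". On top of these, "A subgroup analysis based on gender is also planned to investigate any differences in outcomes between male and female participants".

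Section 6 gives 30 per group "to achieve statistical significance with an alpha of 0.5 and a power of 0.8 for subgroup analysis of the initial trials on PEI", and for the pooled 240 participants "an alpha 0.05 and a power of 0.8 for combined analysis". It treats the populations as equals: "The outcomes to be determined are identical in the four parallel trials to foster comparability across populations". The method named is one- and two-way ANOVA, and sidedness is not stated.

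No section says which test comes first, how alpha is shared, or that the population results are exploratory. Section 3 uses pilot and feasibility language, but also says the study will assess efficacy and effectiveness.

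**The concern.** Each population analysis is sized to reach significance in its own right, so it is planned as a test and not only as description. The combined analysis is a further test of the same program on the same participants. With nothing ranking these tests, a report could put one positive population beside a null combined result and present it as a finding of benefit. Nothing in the plan would rule that out. What is at stake is the false-positive rate over the whole set of tests, and this remains even if the printed subgroup alpha is corrected to 0.05.

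**Working it through.** **Inputs.** From section 6: 75% against 66% days abstinent (difference 9), SD 24, 30 per group, 240 in total, combined alpha 0.05. From section 5: four populations, possibly overlapping. Reading 30 as per arm fits the total: 4 × 2 × 30 = 240. Assumptions: 1:1 allocation, two-sided tests, one outcome, one time point. The documents do not give the overlap, so it is varied.

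**The plan's own figure.** At 30 per arm the standardised effect is 9 / (24 × √(2/30)) = 1.452.
- Two-sided alpha 0.5 (critical value 0.674): Φ(1.452 − 0.674) = 0.782, or 0.798 counting both tails. The stated 0.8 is reproduced at the printed alpha.
- One-sided alpha 0.5 would need only 11 per arm, so the figure fits a two-sided test.
- Two-sided alpha 0.05: Φ(1.452 − 1.960) = 0.306. About 112 per arm would be needed for 0.8.

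**False-positive rate at two-sided 0.05 per test, no true effect.**

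Four disjoint populations: 1 − 0.95⁴ = 0.185 in either direction; 1 − 0.975⁴ = 0.096 in the program's favour.

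The combined test is not independent of these. Two tests that share participants have correlation (number shared) / √(n₁n₂). For a population of 60 inside the pooled 240 this is 60 / √(60 × 240) = 0.5. Treating five tests as independent (1 − 0.95⁵ = 0.226) therefore overstates the rate. Simulation under the null (1 to 2 million draws) gives:

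| Setting | Four, either direction | Plus combined | Four, favourable | Plus combined |
|---|---|---|---|---|
| Disjoint, equal | 0.185 | 0.203 | 0.096 | 0.105 |
| Overlap, correlation about 0.23 | 0.176 | 0.190 | 0.089 | 0.096 |
| Overlap, correlation about 0.29 | 0.172 | 0.185 | 0.087 | 0.093 |
| Overlap, correlation about 0.48 | 0.157 | 0.166 | 0.078 | 0.083 |

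The overlap rows assign each of 240 people to each population with probability 0.25, 0.35 or 0.5, requiring at least one membership.

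**Combined test not significant, at least one population favourable.** In the disjoint case, subtract the chance that the combined test is itself favourable: 0.105 − 0.025 = 0.080, or about 8%. At the heaviest overlap shown, 0.083 − 0.025 = 0.058.

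**Gender.** If men and women were also tested separately, with eight equal population-by-gender cells, the rates would be 0.251 in either direction and 0.130 in the program's favour.

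**Power if population claims were adjusted.** Holm's first step with four tests is 0.05 / 4 = 0.0125 (critical value 2.498): Φ(1.452 − 2.498) = 0.148 at 30 per arm.

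**The case against.** Four points can be made for the plan as it stands.

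- **Parallel trials.** Section 6 calls the populations parallel trials, and the program is meant to be tailored to each. If each population poses its own question, error control within each is defensible. This has weight, and it is why Holm adjustment is optional in the remedy. But the populations may share participants and are pooled in one analysis, so the combined and separate tests still need a stated relation.
- **Pilot with a feasibility focus.** That language in section 3 is general. It is not attached to the population tests, which section 6 sizes for significance.
- **The printed alpha of 0.5 is the real problem.** It is the larger one, and 30 per group depends on it. But correcting it to 0.05 would leave the present gap in place.
- **Gender.** Section 5 describes investigating differences between men and women, which reads as a comparison between genders and not as an efficacy test in each. The objection stands, so the 25% and 13% figures hold only under an assumption.

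A reader might also take the goal in section 7, "The goal of these initial trials is to have CBT4CBT become a standard treatment option in Mental Health and Addictions treatment programs throughout Canada", to mean that a win in any one population counts as success. The text does not say so. It is an aspiration under Risks and Benefits, tied to refined or new versions of the program, and it sets no decision rule.

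**Conclusion.** The gap is real: several significance tests of one program with no hierarchy, adjustment or exploratory label. At two-sided 0.05 per test and no true effect, the chance of at least one false significant result is about 16% to 20%. In the program's favour it is roughly 8% to 11%, against 2.5% for one test. These figures assume one outcome, one time point, 1:1 allocation and test correlations between populations of 0 to 0.5. Section 6 lists several primary outcomes and section 5 plans a six-month follow-up; neither is counted, and further tests on them would raise the rates.

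A reader might infer that an ineffective program would be declared effective in some group 16% to 25% of the time. The documents do not support that. The 16% to 20% counts differences in either direction, and the 25% also needs separate tests in men and women. The favourable rate would be about that high only with one-sided 0.05 tests (14% to 19% for four populations, 19.7% with the combined test if disjoint). Sidedness is not stated, but ANOVA is non-directional and the 30 per group fits a two-sided calculation.

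**What to change.** In section 6, name the combined arm comparison at two-sided 0.05 as the primary test. State that population and gender results are supportive or exploratory, reported as estimates with 95% confidence intervals and without stand-alone efficacy claims. If the sponsor wants population-specific claims, allow them only after a significant combined test and with Holm adjustment over the four populations.

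This changes wording only and needs no extra participants, visits or data. The cost is in what can be claimed. Single-population claims are given up or become hard to reach: for the assumed effect, power at 30 per arm is about 0.31 at 0.05 and about 0.15 at 0.0125, before any loss to dropout.

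### Sections 3 and 5 contradict each other on who delivers the questionnaires and how often; and section 5 schedules 8 in-treatment occasions in the test arm against 2 in control, with no comparison time points set

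*Combined protocol and SAP*

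**What the plan says.** All references are to the combined protocol and SAP.

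**Delivery.** The last paragraph of section 3 (Background, Rationale and Statement of Research Question(s)) has counsellors deliver a questionnaire weekly to their patients in the trial, without distinction by arm. Section 5 (Research Plan) says that a Research Assistant delivers the questionnaires, answered in private on paper or online. The reason it gives is that participants then feel no pressure to show improvement to their counsellor.

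**Schedule.** Under section 5, controls "will also meet with the Research Assistant during week 4 and week 8 to complete questionnaires", and test participants "will also meet with a Research Assistant once a week for eight weeks to complete questionnaires". Both arms are contacted again six months after the eight weeks. On content, section 5 states: "Other than the addition of sections specifically relating to the CBT4CBT program, the questionnaires between groups will be identical". On blinding: "The participant will be notified about the trial arm that they are placed into".

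**Outcome and analysis.** Section 3 makes self-reported abstinence the primary substance use outcome and follows it over the whole study and to six months. Sections 5 and 6 name the primary outcomes and one- and two-way ANOVA, but give no time point for the comparison between arms.

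**The concern.** There are two separate points.

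First, the plan gives site staff two procedures. Under one of them, participants give their account of drug use to the person treating them. Section 5 presents avoiding this as a safeguard, so following section 3 would undo it for an outcome that is purely self-reported.

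Second, one unblinded arm is scheduled to fill in questionnaires four times as often during treatment as the other. Being asked about drug use more often, or meeting study staff more often, can change what people report or how much they use, apart from any effect of the program. If all available forms entered the analysis, the arms would also contribute different weeks.

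**Working it through.** The plan states no figure to reproduce. The check is a comparison of sections and a count.

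**Step 1. Who delivers, and how often.**

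| | Section 3 | Section 5 |
|---|---|---|
| Delivered by | Counsellor | Research Assistant |
| Test arm, in treatment | Weekly | Weekly |
| Control arm, in treatment | Weekly | Weeks 4 and 8 |

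The contradiction on delivery affects both arms. The contradiction on frequency affects controls only: eight weekly forms under section 3, two under section 5.

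**Step 2. Occasions under the section 5 schedule.**

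- Test arm: one per week × 8 weeks = 8; with the six-month form, 8 + 1 = 9.
- Control arm: weeks 4 and 8 = 2; with the six-month form, 2 + 1 = 3.
- Ratio: 8/2 = 4 during treatment; 9/3 = 3 overall.
- Shared occasions: week 4, week 8 and six months = 3.
- Test-only occasions: 9 − 3 = 6 (weeks 1, 2, 3, 5, 6 and 7).
- Gap between successive in-treatment forms: 1 week in test, 4 weeks in control. Items asking about use since the last form would therefore have different recall lengths.

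**Step 3. Do the six test-only forms ask about drug use?** Two statements suggest that they do. Section 3 describes the weekly questionnaire as covering the topics it has just listed, which begin with abstinence. Section 5 makes the forms the same in both arms apart from the CBT4CBT sections. Neither says which items appear in which week. The forms were attached to the protocol but are not in the text available here. Two cases remain:

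- The test-only forms carry drug-use items: arm is confounded with frequency of self-report.
- They carry only CBT4CBT items: drug-use questions are asked equally often, and only the difference in study contact is left.

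**Step 4. Is there a rule on comparison times?** The nearest text is the power paragraph of section 6, which gives percent days abstinent at the end of eight weeks. That describes the earlier trials' results used for planning. It is not an analysis rule for this trial. No section limits comparisons between arms to the three shared occasions.

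**The case against.** **The intended procedure is clear.** Section 5 is the operational section and gives a reason for using the Research Assistant; section 3 is background. This stands, and it makes the correction a short one. It does not remove the conflicting instruction.

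**Comparison at shared times is largely automatic.** Controls have no forms in the other six weeks, so no contrast exists there, and the planning figures refer to week 8. This stands in part. A summary over all available forms is not excluded. A reader might infer that unmatched forms will be pooled, but no passage says so; what is missing is a rule.

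**The extra forms may hold only program items.** This stands as a possibility. A reader might try to settle it from the time burden stated in section 5, which for the test arm is "approximately 45 minutes as a weekly average from participants in the test group"; the control figure is about 10. Those minutes cannot decide it:

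- Control: 10 × 8 = 80 minutes. If all of this goes on two forms, each takes 40 minutes.
- Test, if the 45 includes exactly 30 minutes of program use: (45 − 30) × 8 = 120 minutes. Eight full forms would need 8 × 40 = 320, so the full form at every meeting does not fit.
- Shorter weekly forms with some drug-use items might fit: 120 − 80 = 40 minutes are left for the six test-only meetings. But thirty minutes is a minimum. At an assumed average of 35, the test figure is (45 − 35) × 8 = 80 and nothing is left.

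The protocol itself refers elsewhere for the breakdown: "Please see the consent form table outlining the time commitments in more detail". That table is not available here.

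**Online completion reduces contact.** The test-arm text adds: "These questionnaires can be completed online". This stands for contact with staff, but it does not change how often participants report.

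**Conclusion.** The delivery contradiction holds on the text alone and needs no assumption. So does the schedule of 8 against 2 in-treatment occasions (9 against 3 with six months), and so does the absence of set comparison times.

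Confounding of arm with frequency of drug-use reporting is conditional. It requires drug-use items on the six test-only forms, which sections 3 and 5 make likely and only the attached forms can confirm.

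A reader might infer that the schedule biases the trial in favour of CBT4CBT. The documents do not support that. More frequent questioning could move reported use either way, and nothing in the text gives a direction or a size. Any number of percentage points put on the bias would be an assumption without a source, so none is given. The point should be fixed because the changes are small and the outcome is self-reported in unblinded arms. Confidence is medium, because the attached forms were not seen.

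**What to change.** 1. Amend the section 3 sentence to agree with section 5: outcome forms go through the Research Assistant or online, not the counsellor, and follow the section 5 schedule. Its description of the topics covered can stay.
2. State in section 6 that comparisons between arms on questionnaire outcomes are made only at week 4, week 8 and six months, plus any baseline, with the same recall window in both arms.
3. Limit the test-arm forms at weeks 1, 2, 3, 5, 6 and 7 to the CBT4CBT sections, so that outcome questions are asked equally often. If the attached forms already do this, the protocol need only say so.

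The cost is a short amendment and, under item 3, the loss of weekly outcome data in the test arm. Those data have no control counterpart. With item 2 alone they could be kept as descriptive, but an effect of more frequent assessment or contact would remain. Item 3 equalises the outcome questions; any extra weekly meetings would still differ between arms. The alternative, weekly outcome forms in both arms, would equalise frequency but add six contacts per control participant.
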